### Analysis populations

Efficacy estimates based on intention-to-treat (ITT) analysis set:

All participants will be analysed as randomised.

## Section 5: Trial Population

### Screening data

The following data obtained at the screening visit will be included for those that entered the trial:

- Age
- Self-reported sex
- Self-reported ethnicity
- Self-reported educational level
- Self-reported smoking status and number of years of smoking
- Diabetes duration

### Eligibility

- Age:  $\geq 18$  to  $\leq 75$  years
- Diabetes duration:  $>12$  months
- HbA1c: 53–97 mmol/mol
- Multiple daily insulin injection therapy
- Diagnosed with T1D and treated in a hospital in the Capital Region of Denmark

### Recruitment

The flow diagram of the trial will comply with the most recent CONSORT guidelines for Reporting Outcomes in Trial Reports and includes:

1. Total number assessed for eligibility
2. Total number excluded (numbers not meeting criteria or declined to participate)
3. Total numbers randomised
4. Total number of participants who were randomly allocated to each group
5. The numbers of participants who received and did not receive the allocated treatment in each group
6. The numbers who were analysed for the primary outcomes in each group
8. For each group, losses, and exclusions after randomisation, together with reasons are reported

### Withdrawal/follow-up

The level of consent and consent withdrawal will be tabulated. Participants without HbA1c and MAGE measurements at V2 will be regarded as lost-to-follow-up in relation to the primary outcomes during the intervention period and those with a missing HbA1c measurement at V3 will be regarded as lost-to-follow-up in relation to the primary outcome during the follow-up period. The number of participants lost-to-follow-up for each group during each phase of the trial will be reported in the CONSORT diagram. Summary of baseline levels for variables reported in the baseline table will be provided for completers and for those lost to follow-up/discontinuation of intervention after the baseline visit.

### Baseline participant characteristics

The distribution of all continuous outcomes included in baseline characteristics will be visually inspected using QQ-plots and histograms; those with a Gaussian distribution will be presented as means and standard deviations and those with a non-Gaussian distribution will be presented as medians plus 25th and 75th percentiles, number of observations will be presented for each outcome presented. Categorical data will be summarised by numbers and percentages. Tests of statistical significance will not be undertaken for baseline

characteristics according to the CONSORT Statement for reporting clinical trials; rather the clinical importance of any imbalance will be noted (18).

The following outcomes will be included in the baseline participant characteristics table for all participants combined and stratified by randomisation group:

- Number of participants, n
- Age (years)
- Gender, male, n and %
- Ethnicity, white, n and %
- Smoking status
  - Current smoker, n and %
  - Number of smoking years
- Education
  - Elementary school, n and %
  - Upper secondary education, n and %
  - Vocational, n and %
  - Short further (< 3 y), n and %
  - Medium further (3-4 y), n and %
  - Long further (> 4 y), n and %
- Family status
  - Living alone with or without children at home, n and %
  - Living with a partner with or without children at home, n and %
- Diabetes duration (years)
- HbA1c (mmol/mol)
- Blinded sensor data
  - MAGE (mmol/l)
  - Mean plasma glucose, mmol/l
  - Time in range (TIR): % of readings and time 3.9-10.0 mmol/l
  - Time above range (TAR): % and readings and time 10.1-13.9 mmol/l
  - Time below range (TBR): % readings and time 3.0-3.8 mmol/l
  - Glycaemic variability, coefficient of variation (CV), %
  - Glycaemic variability, standard deviation (SD), mmol/l
- Body weight (kg)
- BMI, kg/m^2
- Waist/Hip ratio, unitless (women)
- Waist/Hip ratio, unitless (men)
- Systolic blood pressure (mmHg)
- Diastolic blood pressure (mmHg)
- LDL cholesterol (mmol/l)
- Glucose-lowering medication
  - Basal insulin dose, units/day
  - Prandial insulin dose, units/day
  - GLP-1, n and %
- Antihypertensives, n and %
- Lipid-lowering medication, n and %
- Use of flash or continuous glucose monitors, n and %

## Section 6: Analysis

### Outcome definitions

#### **Primary outcomes**

HbA1c and MAGE. The treatment effect will be given as the baseline corrected difference in mmol/mol for HbA1c and mmol/l for MAGE between the ACC versus the control group, and the BCC versus the control group at V2.

Estimation of minimal important difference for primary outcome: Reductions in HbA1c of 3.5 mmol/mol and 0.35 mmol/l of MAGE were defined as minimal important differences in this trial. This was based on findings from experimental studies examining the HbA1c effect of BCC (19-21), and meta-analyses of RCTs examining the HbA1c effect of ACC (13-14) vs. control or usual dietary treatment. In these studies, HbA1c reductions between 3 to 7 mmol/mol had been found in adults with T1D. All participants in the studies had a more poorly controlled diabetes (60-108 mmol/mol) than participants eligible for inclusion in our study (53-97 mmol/mol). Consequently, we expected to find smaller HbA1c reductions in our study population. This was considered clinically relevant as part of a multidisciplinary approach for improving glycaemic control in T1D.

#### **Secondary/descriptive/exploratory outcomes**

The treatment effect will be given as the baseline corrected difference between the groups at V2 and V3. No minimal clinically relevant differences were defined for these outcomes.

- HbA1c, mmol/mol (only for V3)
- Blinded CGM data (not measured at V3)
  - Mean amplitude of glycaemic excursions (MAGE), mmol/l
  - Mean plasma glucose, mmol/l
  - Time in range (TIR): % of readings and time 3.9-10.0 mmol/l
  - Time above range (TAR): % of readings and time 10.1-13.9 mmol/l (level 1 – high)
  - Time above range (TAR): % of reading and time >13.9 mmol/l (level 2 – very high)
  - Time above range: % of readings and time >13.9 mmol/l
  - Time below range (TBR): % readings and time 3.0-3.8 mmol/l (level 1 – low)
  - Time below range (TBR): % readings and time <3.0 mmol/l (level 2 – very low)
  - Glycaemic variability, coefficient of variation (CV), %
- BMI (kg/m^2)
- Body weight (kg)
- Waist/Hip ratio, unitless
- Blood pressure
  - Systolic blood pressure (mmHg)
  - Diastolic blood pressure (mmHg)
- LDL cholesterol (mmol/l)
- Median carbohydrate estimation errors, g
- Median carbohydrate estimation errors, %
- Self-reported diabetes diet-related quality of life (DDRQOL), total score within each subscale
  - General perception of diet

- Satisfaction with diet
- Restriction of social functions
- Burden of dietary therapy
- Perceived benefits of dietary therapy
- Mental health
- Vitality
- Self-reported Perceived Health Competence in Diabetes Scale (PCDS), total score
- Self-reported Healthcare Climate Questionnaire (HCCQ) (not measured at V3), total score

### **Other outcomes**

- Number of visits with dietitians, endocrinologists, and diabetes nurses at V2 and V3 in each group.
- Use of bolus calculator to assist insulin dose decision-making in the ACC arm collected after V2.
- Self-reported use of tools to estimate carbohydrate amounts in meals for each group at V1, V2, V3.
- Self-reported frequency and method for estimating mealtime insulin dose for each group at V1, V2, V3.
- Supplementary table with baseline characteristics for completers vs. non-completers with dropout before V2
  - Number of participants, n
  - Age (years)
  - Gender, male, n and %
  - Current smokers, n and %
  - Self-reported educational level
    - o Elementary school, n and %
    - o Upper secondary education, n and %
    - o Vocational, n and %
    - o Short further (< 3 y), n and %
    - o Medium further (3-4 y), n and %
    - o Long further (> 4 y), n and %
    - o Other education, n and %
  - Living alone, n and %
  - Body weight (kg)
  - BMI (kg/m^2)
  - Diabetes duration (years)
  - HbA1c (mmol/l)
- Supplementary table with extra baseline characteristics
  - Occupation
    - o Employed/self-employed, n and %
    - o Unemployed / job seeking, n and %
    - o Retired, n and %
    - o Other (on leave / studying), n and %
  - Annual household income (before tax)
    - o < 100,000 DKK (<13,500 EUR)
    - o 100,000 – 200,000 DKK (13,500 – 27,000 EUR)
    - o 200,000 – 400,000 DKK (27,000 – 54,000 EUR)
    - o 400,000 – 600,000 DKK (54,000 – 81,000 EUR)
    - o 600,000 – 800,000 DKK (81,000 – 108,000 EUR)
    - o 800,000 DKK (>108,000 EUR)
    - o Unspecified
  - Waist circumference, cm (women)
  - Waist circumference, cm (men)

- Fasting concentration of plasma lipids
  - o Total cholesterol (mmol/l)
  - o HDL cholesterol (mmol/l)
  - o Triglycerides (mmol/l)
- Dietary intake
  - o Total energy, kJ/day (women)
  - o Total energy, kJ/day (men)
  - o Carbohydrates, g/day (men)
  - o Carbohydrates, g/day (women)
  - o Carbohydrates, E%
- Physical activity level
  - o Low, n and %
  - o Moderate, n and %
  - o High, n and %
- Supplementary table with baseline-adjusted estimates for other secondary/exploratory outcomes
  - Glycaemic variability, standard deviation (SD), mmol/l
  - Average waist, cm
  - Fasting concentration of plasma lipids
    - o Total cholesterol (mmol/l)
    - o HDL cholesterol (mmol/l)
    - o Triglycerides (mmol/l)
  - Numeracy skills test, correct answers, %
  - Dietary intake (not measured at V3)
    - o Total energy intake (kJ/day)
    - o Carbohydrate intake (E%)
    - o Carbohydrate intake (g/day)
    - o Total fat (E%)
    - o Protein (E%)
    - o Saturated fat (g/day)
    - o Monounsaturated fat (g/day)
    - o Polyunsaturated fat (g/day)
    - o Dietary fibre (g/day)
    - o Dietary fibre (g/10 MJ)
    - o Added sugar (g/day)
    - o Added sugar (g/10 MJ)
  - Self-reported physical activity (International Physical Activity Questionnaire – Short Form (IPAQ SF))
    - o MET-minutes/week
- Supplementary table with delta values for diabetes diet-related quality of life (DDQOL), perceived autonomy support (HCCQ) and competencies in diet and diabetes scale (PCDS)
  - DDQOL subscales (score)
    - o Dietary satisfaction
    - o Dietary benefits
    - o Dietary burden
    - o Social restrictions
    - o General perception of diet
    - o Mental health
    - o Vitality
  - PCDS (total score)
  - HCCQ (total score)

## Analysis methods

Analyses of the primary outcomes will be performed based on efficacy estimates.

Before further analysis and before unblinding, all variables will be inspected to detect outliers to uncover potential errors, such as registration errors.

All continuous outcomes covered by this SAP will as a rule be modelled using baseline corrected repeated measures regression (22) with the following fixed effects and interactions between fixed effects: Visit, Visit (factorial)\*Treatment. Data from V1, V2, and V3 will be included in the analysis. The models will be specified with a restricted maximum likelihood estimation method and a repeat on participant level (unstructured covariance structure). Model fit will be evaluated using graphical methods before estimating the treatment effects and if necessary, outcomes will be log-transformed. Estimated mean differences (CI95%) between groups (CI95%), conditional means (CI95%), and within group changes (CI95%) will be extracted from the model. For log-transformed outcomes the results will be back-transformed and be presented as the ratio between estimated mean differences (CI95%), estimated conditional geometric means (CI95%) and relative changes within groups (CI95%), respectively. If log-transformation cannot meet distribution assumptions, a generalized mixed linear model with an appropriate distribution will be applied instead of the repeated measures regression model. In case the distribution does not comply with the distributions available in the generalized mixed linear model a non-parametric test will be used to compare the change scores for the given outcome.

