9.1.2 Secondary outcomes

Changes in HbA1c from baseline to end-of-treatment (week 12) and at 6-months follow-up (week 48) between and within each of the three study groups (BCC, ABC-ACC and control).

Changes from baseline to end of intervention period (week 24) and at 6-month follow-up (week 48) between and within the three groups (BCC, ABC-ACC and control) in:

- Body weight
- Blood pressure
- Lipid profile: low-density lipoprotein cholesterol (LDL-C), high-density lipoprotein cholesterol (HDL-C), total cholesterol (TC), free fatty acids (FFA) and triglycerides (TG)
- Waist and hip circumference
- Mathematical literacy skills
- Carbohydrate estimation accuracy
- Self-reported diet-related quality of life, perceived competencies in diabetes, health-care climate and physical activity

Changes from baseline to end-of-intervention period (week 24) between and within the study groups in:

- Other parameters of plasma glucose variability including time in range (3.9-10.0 mmol/l), % time spent in hypoglycaemia (<3.9 mmol/l), % time spent in hyperglycaemia (e.g. >11.1 mmol/l) and standard deviation of mean plasma glucose
- Body composition
- Dietary intake (total energy, intake of carbohydrate, fat, protein, added sugar and dietary fibre)

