10.2 Blood Samples

Participants must attend V1, V5 and V6 after 8-10 hours of fasting having consumed only water for collection of blood samples. A small venous catheter will be inserted in one of the participant's arms for blood sampling which will be performed by a trained biomedical laboratory technician in the Clinical Biochemical Department at SDCC. The samples will be used for assessment of C-peptide, triglycerides, total cholesterol, HDL-C, LDL-C, very-low-density-lipoprotein cholesterol (VLDL-C), HbA1c, haemoglobin, creatinine, albumin, potassium, sodium, alanine aminotransferase (ALAT), thyroid-stimulating hormone (TSH), cobalamin and alkaline phosphatase according to standard procedure. No tobacco smoking is allowed in the morning before the visit. HbA1c will also be measured at V4.

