11.6 V4: Intervention, day 3 (week 12)

At visit 4 the following procedures and assessments will be performed:

- Collection of blood sample (non-fasting condition)
- Update of glucose- and lipid-lowering medicine
- Measurement of body weight (non-fasting condition)
- BCC: group-based education activities according to curriculum delivered by two dietitians
- ABC-ACC: individual follow-up with a dietitian
- Control: individual dietary counselling follow-up by a dietitian

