13.1 Calculations

The average changes after week 12, 24 and 48 in primary and secondary outcomes will be calculated for each of the three groups. Results will be presented as means (SD) for normally distributed variables and as medians (inter-quartile range) for non-normally distributed variables.

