### Hypotheses for the primary outcomes:

1. We hypothesize that ACC is superior compared with usual dietary care (the control group) in reducing HbA1c or MAGE from baseline to end-of-treatment at week 24 (from V1 to V2).

Superiority is claimed if:

- a. the 95% confidence interval for the estimated difference in change between the groups for HbA1c or MAGE, estimated using a baseline corrected linear mixed model, excludes 0 and the P-value is <0.05: and,
- b. the estimated difference in HbA1c or MAGE between the two groups is equal to/surpass the minimal important difference in favour of the ACC group.

2. We hypothesize that BCC is superior compared with usual dietary care (control group) in reducing HbA1c or MAGE from baseline to end-of-treatment at week 24 (from V1 to V2).

Superiority is claimed if:

- c. the 95% confidence interval for the estimated difference in change between the groups for HbA1c or MAGE, estimated using a baseline corrected linear mixed model, excludes 0 and the P-value is <0.05: and,
- d. the estimated difference in HbA1c or MAGE between the two groups is equal to/surpass the minimal important difference in favour of the BCC group.

3. We hypothesize that BCC is equivalent to ACC in reducing HbA1c or MAGE from baseline to end-of-treatment at week 24 (from V1 to V2).

Equivalence is claimed if:

- e. The 90% confidence interval for the estimated difference in change between the groups for HbA1c or MAGE does not surpass minimal important difference in a negative or positive direction (16).

Hypotheses for the secondary outcomes can be found in the study protocol and [clinicaltrials.gov](https://clinicaltrials.gov).

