### Timing of outcome assessments

HbA1c was measured at the screening visit (V0), at the baseline visit (V1), after 12 weeks of intervention, after 24 weeks (V2) of intervention, and after six months follow-up (V3). MAGE was measured after the baseline visit (V1), and after 24 weeks of intervention (after V2).

See section 6: Analyses for timing of secondary/descriptive/explorative outcome assessments.

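### The SAP leaves week-12 HbA1c, a protocol secondary outcome that was collected, out of both its HbA1c model and its outcome list

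*SAP*

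**What the plan says.** The two documents number visits differently. In the protocol, V4 is week 12, V5 week 24 and V6 week 48. In the SAP, V2 is week 24 and V3 the six-month follow-up, and week 12 has no visit label.

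- **Protocol 9.1.2** lists among the secondary outcomes "Changes in HbA1c from baseline to end-of-treatment (week 12) and at 6-months follow-up (week 48".
- **Protocol 10.2** schedules the sample: "HbA1c will also be measured at V4". Section 11.6 is headed "V4: Intervention, day 3 (week 12" and is the last education visit.
- **Protocol 13.1**: "The average changes after week 12, 24 and 48 in primary and secondary outcomes will be calculated for each of the three groups".
- **Protocol 13.2** gives a general method for all primary and secondary outcomes: intention-to-treat, general linear models, last observation carried forward.
- **SAP Section 3, Timing of outcome assessments**, confirms collection: "HbA1c was measured at the screening visit (V0), at the baseline visit (V1), after 12 weeks of intervention".
- **SAP Section 6, Analysis methods**, restricts the repeated-measures model: "Data from V1, V2, and V3 will be included in the analysis".
- **SAP Section 6, Secondary/descriptive/exploratory outcomes**, has the entry "HbA1c, mmol/mol (only for V3". Week-12 HbA1c is not in the primary definition or under Other outcomes either.
- **SAP Section 6, Missing data**, relies on likelihood estimation under missing at random. Additional analyses are marked as not relevant.

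**The concern.** Two things follow from the omission.

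First, a secondary outcome named in the protocol has no place in the SAP. The SAP replaces the protocol's method with a mixed model, but does not say which method applies to week 12 or whether week 12 counts in the false discovery rate correction of SAP Section 4.

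Second, the primary HbA1c contrast is touched. Missing at random is an assumption given the data in the model. Someone who attends week 12, then leaves and does not return, has a week-24 value predicted from baseline alone, although a later HbA1c is on file. If leaving depends on how HbA1c had responded by week 12, and does so differently by arm, the week-24 contrast is biased.

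A modest bias can matter because the superiority rule has a condition on the point estimate: "the estimated difference in HbA1c or MAGE between the two groups is equal to/surpass the minimal important difference in favour of the ACC group". The same condition applies to BCC.

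**Working it through.** **1. The plan's own figure, which fixes the scale.** Protocol 13.3 uses a difference of 3.5 mmol/mol, SD of change 7, two-sided 5% and 80% power. The two-sample t-test needs 63.8, so 64 per arm (power 0.801). Then 3 × 64 = 192, and 64 × 1.2 = 76.8, so 77 per arm and 231 in total. The figure reproduces, and SD 7 is used below.

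**2. Assumptions not in the documents.** Correlation between V1 and later visits (ρ) is 0.7 or 0.8, and between later visits 0.85 or 0.9. Level SD = 7/√(2(1−ρ)), so level variance is 49/0.6 = 81.67 or 49/0.4 = 122.5. The true effect is −3.5 at week 12, V2 and V3. Dropout after week 12 is logistic in the week-12 change, with log-odds slope +0.8 or −0.8 per 7 mmol/mol. Each setting has 300,000 simulated per arm. The model is the SAP's baseline-constrained one, with known covariance. Bias is the estimate minus the full-data estimate.

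**3. Bias in the week-24 contrast without week 12 (mmol/mol).**

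| Loss after week 12, by arm | None return at V3 | Half return | All return |
|---|---|---|---|
| 10% vs 5% | about 0.14-0.17 | about 0.10 | about 0.03-0.05 |
| 20% vs 10% | about 0.25-0.35 | 0.16-0.19 | 0.06-0.11 |
| Equal rates, same slope | about 0 | about 0 | about 0 |

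If poor responders leave and control loses more, the benefit is understated. If good responders leave, or if poor responders leave and the active arm loses more, it is overstated by a similar amount. With week 12 in the model the bias is within 0.02 of 0, by construction, because dropout then depends only on modelled data.

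Equal rates alone do not guarantee this. With 20% lost in each arm but dependence in the treated arm only (log-odds 0.5 to 1.1 per SD, V1 to week-24 correlation 0.50-0.75), a true −3.5 is estimated as −3.8 to −4.4 without week 12.

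**4. What week 12 cannot repair.** If dropout depends on the unseen week-24 change (20% vs 10%, none returning), the bias is 0.41-0.45 without week 12 and 0.15-0.30 with it. The share removed runs from 1 − 0.292/0.441 = 34% to 1 − 0.148/0.413 = 64%.

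**5. Precision.** Take 77 per arm and 20% lost by week 24, of which 7.5 points fall after week 12. Then 77 × 0.8 = 61.6 per arm have a week-24 value. SE = √(2 × level variance × (1−ρ²)/61.6):
- ρ = 0.7: √(2 × 81.67 × 0.51/61.6) = 1.16
- ρ = 0.8: √(2 × 122.5 × 0.36/61.6) = 1.20

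Adding week 12 lowers the SE by 0.9-2.8% (later-visit correlations 0.8-0.9).

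**6. The point-estimate condition, HbA1c only.** At a true effect of exactly 3.5, the chance that the estimate reaches 3.5 is 50% without bias. Take a bias of 0.13-0.17, which allows for simulation error at the lower end:
- Φ(−0.13/1.20) = 0.457 and Φ(−0.17/1.16) = 0.442, so about 44-46% if the benefit is understated
- about 54-56% if it is overstated

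**The case against.** The strongest reply has five parts.

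- **A method exists.** A reader might infer that week 12 has no analysis anywhere, or that the outcome was deliberately removed. The documents do not support either. Protocol 13.1 and 13.2 cover it in general terms, and the SAP sends the reader to the protocol for secondary hypotheses. What stands is narrower: the SAP did not carry the outcome over, and the protocol's method differs from the SAP's.
- **Response-driven, unequal dropout is assumed.** The documents report only about 20% dropout overall. Protocol 9.5.3 plans follow-up of withdrawn participants at study end where they agree, and V3 is in the model. The larger biases need all the loss to fall after week 12 with nobody returning. This stands, and it is why the 10% vs 5% row is the main illustration.
- **The 50% figure is fragile.** A reader might take step 6 as the chance of a superiority claim. It is not: the rule accepts HbA1c or MAGE and also requires significance, and a true effect of exactly 3.5 is where sensitivity is greatest. At a true effect of 0, even a bias of 0.33 moves the chance of reaching 3.5 by less than 0.3 percentage points.
- **Safeguards exist.** The SAP reports missing primary values by group and time point, compares baseline data of completers and those lost, and reports exclusions by arm. These would show unequal loss, but would not correct for it.
- **Week 12 might be a slip for week 24 in Protocol 9.1.2,** since it is called end of treatment there. This fails: week 24 is already primary, and 10.2, 13.1 and Tables 1 and 4 all include week 12.

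**Conclusion.** The omission is real and should be corrected before analysis. The reporting gap needs no assumption: a protocol secondary outcome, measured and planned for calculation, is in neither the SAP model nor its lists. The effect on the primary HbA1c contrast is a possibility, not a demonstrated bias. It is about 0.14-0.17 mmol/mol under 10% vs 5% response-dependent loss with none returning, 0.03-0.05 if all return, and up to about 0.35 at 20% vs 10%, against an SE of 1.16-1.20. It rests on assumed dropout and correlations. The precision gain is about 1-3%. MAGE was not measured at week 12 and is unaffected.

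A related wording point is separate. SAP Section 4 excludes people lost before baseline measurements, while the SAP's Randomisation section, protocol Table 1 and protocol 11.2 place randomisation at screening. A reader might infer that this biases the primary result. The exclusion is openly stated, and it changes no estimate unless those people have later HbA1c or MAGE values. It is a matter of labelling the analysis set.

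**What to change.** In SAP Section 6:

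1. For HbA1c, include V1, week 12, V2 and V3 in the repeated-measures model, with week 12 as a post-baseline level of Visit and Visit*Treatment. MAGE stays with V1 and V2.
2. Change the HbA1c entry in the secondary list to cover week 12 and V3, and report the week-12 contrast from the same model.
3. State that this contrast belongs to the false discovery rate family.

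Cost: the unstructured HbA1c covariance grows from three visits to four (3 × 4/2 = 6 parameters to 4 × 5/2 = 10), and the week-12 contrast joins the false discovery rate family. No new data, visits or participants are needed.

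Wording only: in SAP Section 4, either drop the exclusion of people lost before baseline or call the set modified intention-to-treat. Reconcile protocol 9.6 and 9.8, which place randomisation at V1, with protocol Table 1, protocol 11.2 and the SAP's Randomisation section.

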13.3 Determination of sample size

Allowing for drop-outs (~20%) and subgroup analyses we plan to include a total of 231 patients in our study. This is based on sample size calculations which suggested that including 64 participants in each of the study groups would give us 80% power to detect a clinically meaningful difference in change in HbA1c of 3.5 mmol/mol between the BCC group versus the control group or the ABC-ACC group versus the control group with a 5% significance level using a two-sided test and an estimated standard deviation (SD) of 7 mmol/mol. This SD has previously been used for sample size calculations in ACC trials (28) and was similar to what we found in our evaluation of our BCC courses on mean changes and SD of HbA1c after 6 months in completers with T1D (n=185). MAGE has only been used as an outcome measure of glucose variability in a few randomized controlled dietary intervention studies of patients with diabetes (42, 43) showing differences in changes in MAGE up to 4.8 mmol/l (SD: 1.0) after a 12-week carbohydrate counting intervention (42). By including 77 participants in each study group we will have a power of 80% (alpha level of 0.05) in a two-sided test to detect a clinically meaningful difference in the change in MAGE during the intervention period (week 24) of ≥ 0.35 mmol/l (SD 0.7 mmol/l) between the study groups as presented in **Table 5**.

Table 5: Sample size calculations

Difference in HbA1c, mmol/mol (SD 7.0)	Difference in MAGE, mmol/l (SD 0.7)	Net total no of participants in the study (BCC group vs control or ABC-ACC group vs control)	No of participants given a dropout rate of 20%
2.0	0.20	582	698
3.0	0.30	261	315
3.5	0.35	192	230
4.0	0.40	150	180

14 Data management

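### The SAP's last-resort test of change scores names no baseline adjustment, estimate or interval, and is usually less efficient than a baseline-adjusted rank analysis

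*SAP*

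**What the plan says.** The SAP section Analysis methods sets four steps for all continuous outcomes:

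1. A baseline-corrected repeated measures model.
2. Log-transformation, if the fit is poor.
3. A generalized mixed model with a suitable distribution.
4. If none fits, "a non-parametric test will be used to compare the change scores for the given outcome".

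Step 4 names no test, baseline term, effect estimate, interval or rule for missing visits.

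Elsewhere the SAP defines effects differently. Under Primary outcomes, the effect for HbA1c and MAGE is a baseline-corrected difference in the outcome's units. For the remaining outcomes, "The treatment effect will be given as the baseline corrected difference between the groups at V2 and V3". Section 4 promises P-values and 95% confidence intervals for comparisons between groups. The Missing data section relies on likelihood estimation in the linear mixed model.

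The secondary list includes "Time below range (TBR): % readings and time <3.0 mmol/l (level 2 – very low"). The Harms section says that harms are not systematically collected and will not be reported.

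Protocol 13.2 has a shorter fallback: non-parametric tests if log-transformation does not rescue the model assumptions.

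**The concern.** The step 4 wording does not deliver what the rest of the SAP promises. A rank test of changes gives a P-value about the ordering of changes. It does not give a baseline-corrected difference with an interval.

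Subtracting baseline in full is also not the same as adjusting for it. Unless the correlation between baseline and follow-up is high, the change score carries the baseline's noise into the outcome and power falls. A change score needs both visits, so the likelihood handling of missing data no longer applies, and the protocol plans for about 20% dropout.

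The outcomes most likely to be awkward are those with many zeros. Zeros cannot be logged, and they lie outside the range of standard gamma and beta models. Time below 3.0 mmol/l is the obvious example. Because harms are not reported separately, the low-glucose sensor outcomes are the main information on hypoglycaemia. If such an outcome reached step 4, a real change in either direction could more easily be reported as no difference, although the baseline values are already collected.

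**Working it through.** **1. The plan's own sample size.** Protocol 13.3 states that "including 64 participants in each of the study groups would give us 80% power". The inputs there are a target of 3.5 mmol/mol for HbA1c, SD 7 mmol/mol and a two-sided 5% test. The standardised effect is 3.5/7 = 0.5. The normal formula gives n = 2(1.960 + 0.842)²/0.5² = 62.8, so 63 per arm. The t-test gives 63.8, so 64, with power 80.1%. The plan's figure reproduces.

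**2. Number analysed.** "Allowing for drop-outs (~20%) and subgroup analyses we plan to include a total of 231 patients", which is 77 per arm. With 20% dropout, 77 × 0.8 = 61.6, taken as 62.

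**3. Why change scores cost power.** Let σ² be the variance at each visit and ρ the baseline to week-24 correlation.
- Variance of change: 2σ²(1 − ρ).
- Variance after baseline adjustment: σ²(1 − ρ²).
- Relative efficiency of change: (1 − ρ²)/[2(1 − ρ)] = (1 + ρ)/2, which is 0.65 at ρ = 0.3, 0.75 at 0.5 and 0.90 at 0.8.

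A Wilcoxon test on normal data adds a factor 3/π = 0.955. If the adjusted analysis has 80% power (noncentrality 2.80), then at ρ = 0.5 the change-score rank test has Φ(2.80 × √(0.955 × 0.75) − 1.96) = 65.9%, a loss of 14.1 points. The loss is 20.2 at ρ = 0.3 and 6.2 at ρ = 0.8. This shows the mechanism only, because normal data would never reach step 4.

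**4. Zero-inflated data.** Assumptions, none of them in the documents: a latent bivariate normal with correlation ρ, left-censored to 20% or 40% zeros and exponentiated; 62 per arm; a 0.5 SD latent shift at follow-up. The comparison is Mann-Whitney on change against regression of ranked follow-up on arm and ranked baseline. Power in %, change-score test vs adjusted test, 2,000 runs per cell, loss in brackets:

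| Direction | ρ | 20% zeros | 40% zeros |
|---|---|---|---|
| Increase | 0.2 | 55 vs 78 (23) | 55 vs 75 (20) |
| Increase | 0.4 | 68 vs 84 (16) | 65 vs 78 (13) |
| Increase | 0.6 | 84 vs 91 (7) | 81 vs 86 (5) |
| Decrease | 0.2 | 43 vs 75 (32) | 37 vs 69 (32) |
| Decrease | 0.4 | 54 vs 80 (26) | 46 vs 74 (28) |
| Decrease | 0.6 | 71 vs 89 (18) | 62 vs 82 (20) |
| Decrease | 0.8 | 91 vs 98 (7) | 84 vs 94 (10) |

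The spread of the non-zero values is a further assumption, and repeat runs of the design differ by several points, mainly for decreases. The run with the largest losses gave these results:
- Increase: 16-22 points at ρ = 0.2-0.4, 9 at 0.6 and 1 at 0.8.
- Decrease: 31-35, 26-27 and 10-16 points at the same correlations.

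Another run gave 22-29 points at 0.2-0.3, 11-23 at 0.6 and 2-10 at 0.8 for a decrease. Type I error was about 4-6% for both tests.

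**5. Other shapes.** With 64 per arm, an effect of 0.5 SD of change and ρ from 0.3 to 0.8, the loss against a baseline-adjusted rank test (Quade) was:
- 2.9 to −0.8 points for bivariate t with 3 degrees of freedom;
- 10.6 to −3.5 points for a normal baseline with t3 residuals;
- about zero for lognormal data, where power was near its ceiling and step 2 would normally suffice.

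A negative figure means that the change-score test did better.

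**The case against.** **The step may never be used.** It comes fourth. Time below 3.0 mmol/l is a percentage of readings, so it derives from a count. Binomial, Poisson and negative binomial models accept zeros, and an ordinal model handles ties at zero. SAS and R, both named in the SAP, offer these. This stands: a reader might infer that the hypoglycaemia outcomes will be tested by change scores, but neither document shows that any outcome reaches step 4. HbA1c and MAGE fall formally within its scope, but nothing suggests that they would get there.

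**Change scores do not ask a different question.** A reader might infer a bias or a wrong target. Under randomisation, the mean difference in change and the baseline-corrected mean difference estimate the same quantity, and the SAP's own hypotheses speak of a difference in change. The shift in target comes from using ranks, which a rank-based replacement also does. This stands.

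**No adjustment is inferred from silence.** The SAP does not rule out an adjusted test. That is correct, but a test described only as comparing change scores would ordinarily be read as unadjusted, so the wording needs settling.

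**Adjustment alone does not cure everything.** A rank or ordinal model with baseline as covariate also needs both visits, and it gives no difference in the outcome's units. This stands too, so the fix needs a rule for missing visits.

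**Stakes are limited.** These outcomes are labelled secondary, descriptive or exploratory, with no minimal relevant difference. That lowers the priority but does not remove the gap.

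**Conclusion.** The concern holds in a limited form. Step 4 is underspecified and does not match the SAP's stated effect measure, because no baseline covariate, estimate or interval is given. It is a valid test, so the cost is efficiency and interpretability and not false positives.

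Under the zero-inflated assumptions the change-score test was less powerful in every cell, by about 1 point (increase, ρ = 0.8) to about 35 points (decrease, ρ = 0.2). No single figure such as 10 to 20 points is supportable. The loss depends on a correlation that the documents do not give, on the direction of the effect and on the shape of the data, and for some heavy-tailed shapes it disappears.

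All of this is conditional on an outcome failing the three earlier steps. Priority is minor to moderate.

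**What to change.** Replace the last sentence of the SAP's Analysis methods section with:

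> If no available distribution fits, the V2 (or V3) value will be compared between arms with a baseline-adjusted rank or ordinal method (e.g. a proportional-odds model with baseline as covariate, or rank ANCOVA), reported with an effect estimate and 95% CI. The number of participants excluded for missing V1 or follow-up values will be reported (or those values will be multiply imputed under MAR).

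The cost is one or two sentences. The methods use baseline values already collected and run in the software already named. The drawback is that the effect is on an odds or rank scale and not in the outcome's units. Without imputation, participants lacking either visit still drop out of the analysis. The SAP places the analyses after its own upload, so the wording should be settled before then.
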